Administration of lapatinib to rats and dogs for up to 6 months or 9 months resulted primarily in exaggerated pharmacologic effects and organ toxicities generally associated with degenerative and/or inflammatory epithelial changes (GI tract and accessory digestive organs, skin, mammary gland, liver and prostate).⁶⁵ Other treatment-related effects included clinical signs, decreased body weight and food consumption, organ weight changes and alterations in clinical pathology parameters. Following the recovery period, treatment-related changes were either significantly improved or completely reversed. There were no effects on male or female rat gonadal function, mating, fertility or pregnancy nor were there any increases in the number or incidence of any malformations when rats or rabbits were given lapatinib during the period of major organogenesis. At maternally toxic doses (□60 mg/kg/day in rats and rabbits), lapatinib treatment was associated with growth retardation and developmental variations. In genetic toxicity studies, lapatinib was demonstrated to be non-mutagenic and nonclastogenic.

Lapatinib Pharmacokinetics The pharmacokinetics of lapatinib are similar in healthy volunteers and patients, demonstrating oral absorption that is incomplete, highly variable, and sometimes delayed.⁶⁵ After dosing, plasma concentrations rise to a peak at approximately 4 h and thereafter decline with measured half-lives averaging up to 14 h. However, accumulation with daily dosing achieves steady state in 6-7 days, which suggests a true elimination half-life on the order of 24 h. Administration of the same daily dose in a BID schedule results in 2-fold greater systemic exposure than a QD schedule. Despite this inconsistency, systemic exposure generally increases with increasing dose. Absorption is increased by ingestion with food. Elimination of lapatinib is predominantly through metabolism by CYP3A4/5 with negligible renal excretion. Significant changes in systemic exposure to lapatinib result from co-administration of drugs that are potent inhibitors or inducers of CYP3A.

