Lapatinib Safety Safety results from Phase I monotherapy studies in cancer patients indicate that lapatinib administered on a QD schedule was generally well tolerated at doses of lapatinib ranging from 175 mg to 1800 mg QD. Doses of 500 and 750 BID were better tolerated than 900 mg BID.⁶⁵ The majority of AEs were Grade 1 or 2 gastrointestinal and/or skin toxicities. The incidence of diarrhea increased with increasing dose, whereas the incidence of rash was not related to dose. The Phase II/Phase III program had enrolled a total of 1581 subjects. Of these, 1001 subjects were enrolled in Phase II monotherapy studies. Data suggest that lapatinib administered as monotherapy at doses of 1250 mg QD, 1500 mg QD, and 500 mg BID is generally well tolerated. For the completed and ongoing Phase II and Phase III studies, the preliminary safety data was similar to what has been observed in the Phase I monotherapy studies and combination studies. The most common AEs considered related by the investigator were gastrointestinal (diarrhea, nausea, vomiting), rash, fatigue, and anorexia. The majority of all AEs were Grade 1 and Grade 2.

SAE data from ongoing lapatinib studies (all phases) are from 2312 subjects treated with lapatinib.⁶⁵ For the ongoing studies, a total of 831 SAEs were reported from 405 individual subjects. The most frequently reported SAE was diarrhea, with a total of 47 reports, 37 of which were assessed as related to investigational product. Dyspnea, vomiting, dehydration, and nausea were also among the most frequently reported SAEs regardless of relatedness. Overall, 24.6% of the SAEs reported were assessed as related to investigational product by the investigator. The most frequently reported drug-related events were: diarrhea, neutropenia, vomiting, nausea, dehydration, and decreased ejection fraction. Diarrhea which may lead to dehydration, nausea, and vomiting are all included in the development core safety information for lapatinib. Interstitial pneumonitis and two cases of interstitial pneumonia have been reported in the lapatinib program. Subjects on the lapatinib program have experienced a decrease in LVEF, giving an approximate incidence for this event of 1.4%.

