3.0 STUDY DESIGN (Table 1 and Figure 7)

The study is an open-label, single arm, single institution, pilot clinical trial of Veliparib (a PARP inhibitor) in combination with Lapatinib (an EGFR inhibitor) in patients with pathologically confirmed TNBC (ER negative, PR negative, HER-2-Neu negative by IHC [0, 1] or FISH) who have not received prior therapy in the metastatic setting (but failed anthracyclines and taxanes in the

neoadjuvant or adjuvant setting) or who have failed prior chemotherapy in the metastatic setting (including anthracyclines and taxanes and no more than two prior regimens for metastatic disease as long as patients have adequate performance status – see Appendix B). The data obtained in this pilot study will be used to design a phase II clinical trial that will be conducted by the Translation Breast Cancer Research Consortium.

As described in **Figure 7**, patients will receive Lapatinib (1250 mg PO daily continuously) in combination with Veliparib (200 mg PO every 12 hours continuously). A cycle of therapy is defined as 28 days of PO therapy. Lapatinib will start Day 1 cycle 1 and Veliparib will start on Day 2 Cycle 1 (for better understanding of the PK of the drugs as well as to induce a DSB repair defect first with Lapatinib). Dose reductions of Lapatinib and Veliparib will be allowed. Patients developing grade 1 and 2 toxicities will be permitted to take a drug holiday of up to 14 days; after the drug holiday, if the adverse event has resolved to the satisfaction of the investigator, the study drugs may be resumed at the same level. In the event of recurrent toxicity, there will be two dose reductions permitted (dose reduction minus one will be Lapatinib 1000 mg PO daily continuously and Veliparib 150 mg PO every 12 hours continuously); dose reduction minus two will be Lapatinib 750 mg PO daily and Veliparib 100 mg PO every 12 hours continuously. If the adverse event recurs after dose reduction two, the patient will be taken off the study. Patients developing grade 3 and 4 toxicities will be interrupted for up to 14 days; after the drug holiday, if the adverse event has resolved to the satisfaction of the investigator, the study drugs may be resumed at a reduced dose (Lapatinib 1000 mg PO daily continuously and Veliparib 150 mg PO every 12 hours continuously). If the adverse event recurs, the patient will be taken off the study.

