This rule will provide a probability of 0.10 of stopping early if the true toxicity rate is 30%. In that case the expected number of subjects on the trial will be 18.87 and the expected number of toxicities will be 5.7. If, on the other hand, the true toxicity rate is 60%, then the probability of stopping early is 0.87 with an expected sample size of 9.8 and 5.9 expected toxicities. Table 2 is the stopping guideline if 'X' out of 'N' has a pre-defined toxicity. As an example, if we enroll 3 patients and all have toxicity, then we will consider stopping the trial; if we enroll 6 patients and 5 patients have toxicity then the trial will be stopped.

Drug related toxicities for the safety analysis described above are defined as: a) any grade 3 or 4 non-hematologic toxicity except anorexia, alopecia, nausea, fatigue, fever without neutropenia; b) failure to recover to baseline (except alopecia) after delaying the next dose by more than 14 days; c) grade 3 or 4 neutropenia complicated by fever $\geq 38.5^0$ C or infection, or grade 4 neutropenia of at least 7 days duration; or d) grade 4 thrombocytopenia, or grade 3 thrombocytopenia complicated by hemorrhage. Toxicity evaluation of the patients enrolled in the trial will be done using the NCI Common Toxicity Criteria, Version 4.0, and will be presented to the Clinical Protocol Monitoring Committee (UAB Safety and Monitoring Plan).

If toxicity meets the stopping rule at any time during the first 5 patients enrolled in the pilot study (see table 2), the protocol will allow the investigators to open a new 20 patient cohort using Lapatinib 1000 mg PO a day and Veliparib 150 mg PO twice a day. The new cohort will follow the same rules used in the original cohort (Cohort -1). Patients developing grade 1 and 2 toxicities will be permitted to take a drug holiday of up to 14 days; after the drug holiday, if the adverse event has resolved to the satisfaction of the investigator, the study drugs may be resumed at the same level. In the event of recurrent toxicity, there will be one dose reduction permitted (dose reduction minus one will be Lapatinib 750 mg PO daily continuously and Veliparib 100 mg PO every 12 hours continuously). If the adverse event recurs after dose reduction two, the patient will be taken off the study.

Patient Selection Criteria

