5.2.3 Lapatinib Dosing

The daily dose of Lapatinib will be 1250 mg PO every 24 hours continuously for 28 days (a cycle). Patients developing grade 1 and 2 toxicities will be permitted to take a drug holiday of up to 14 days; after the drug holiday, if the adverse event has resolved to the satisfaction of the investigator, the study drug may be resumed at the same level. In the event of recurrent toxicity, there will be two dose reductions permitted (Lapatinib 1000 mg PO every 24 hours continuously and Lapatinib 750 mg PO daily). If the adverse event recurs, the patient will be taken off the study. Patients developing grade 3 and 4 toxicities will be permitted to take a drug holiday of up to 14 days; after the drug holiday, if the adverse event has resolved to the satisfaction of the investigator, the study drugs may be resumed at a reduced dose (Lapatinib 1000 mg PO every 12 hours continuously). If the adverse event recurs, the patient will be taken off the study. Lapatinib will start on day 1.

Patients should be carefully instructed by study personnel on how to take lapatinib. Patients will be instructed to take lapatinib, 1250 mg (5 tablets) PO on a daily basis, at approximately the same time each day. Lapatinib must be taken on an empty stomach—either 1 hour (or more) before a meal or 1 hour (or more) after a meal. Patients may not use anything but water to help them swallow their lapatinib. Medications that modify gastric pH, while not prohibited, are restricted and further described in the table of prohibited medications. Histamine H₂ antagonists and proton pump inhibitors are allowed. NOTE: Lapatinib is not to be taken with grapefruit or grapefruit juice. Grapefruit and grapefruit juice should not be taken at any time during the study. If the patient vomits after their lapatinib dose, the patient should be instructed not to retake the dose. Patients should take the next regularly scheduled dose of lapatinib. If vomiting persists, the patient should contact their study doctor.

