APPENDIX I

Diarrhea Management Guidelines

Diarrhea Management Guidelines

Background

Experience thus far suggests that when lapatinib is used as monotherapy 51% of patients experience diarrhea; most diarrhea presents as uncomplicated NCI CTCAE Grade 1 or 2 (G1 30%, G2 15%, G3 6%, G4<1%) (Crown, 2008).

In rare cases, diarrhea can be debilitating, and potentially life threatening if accompanied by dehydration, renal insufficiency, and/or electrolyte imbalances.

Standardized and universal guidelines have been developed by an American Society of Clinical Oncology (ASCO) panel for treating chemotherapy-induced diarrhea (Benson, 2004). Presented in the sections below are the recommended guidelines for the management of diarrhea in subjects receiving lapatinib-based therapy; these guidelines were derived from the recommendations published by the ASCO panel (Benson, 2004).

Early identification and intervention is critical for the optimal management of diarrhea. A subject's baseline bowel patterns should be established so that changes in patterns can be identified while subject is on treatment.

It is strongly recommended to give subjects receiving lapatinib-based therapy a prescription of loperamide with instructions to start loperamide at the onset of diarrhea as per the recommendations outlined below. Subjects should be instructed to first notify their physician/healthcare provider at onset of diarrhea of any severity.

An assessment of frequency, consistency and duration as well as knowledge of other symptoms such as fever, cramping, pain, nausea, vomiting, dizziness and thirst should be taken at baseline. Consequently subjects at high risk of diarrhea can be identified. Subjects should be educated on signs and symptoms of diarrhea with instructions to report any changes in bowel patterns to the physician.

It is recommended that subjects keep a diary and record the number of diarrhea episodes and its characteristics. They should also include information on any dietary changes or other observations that may be useful in the evaluation of their diarrhea history.

If subjects present with diarrhea of any Grade, check they are taking lapatinib correctly, i.e. single daily dose, rather than splitting it through the day. Obtain information on food (solid and liquid) and over the counter (OTC) medication, including herbal supplements, taken during the lapatinib treatment period.

Definitions

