IV. Recurrent Diarrhea (more than 1 occurrence of Grade 2 diarrhea): once the 2nd occurrence of Grade 2 diarrhea resolves to \leq Grade 1, consider reducing the dose of lapatinib by 250mg or 1 tablet, unless the lapatinib dose already had been reduced to 750mg. No further dose reduction is recommended for subjects taking lapatinib at 750mg.

2. Consider a dose reduction for chemotherapy (if applicable)

B) Complicated Diarrhea

I. CTCAE Grade 3 or Grade 1 or 2 with complicating features (severe cramping, severe nausea/vomiting, decreased performance status, fever, sepsis, Grade 3 or 4 neutropenia, frank bleeding, dehydration)

1. Subject **must** call physician immediately for any complicated severe diarrhea event
2. If loperamide has not been initiated, initiate loperamide immediately: Initial dose 4mg followed by 2mg every 2 hours or after every unformed stool*
3. Refer to the dietary modification recommendations for Grade 1 and Grade 2 uncomplicated diarrhea
4. For dehydration use intravenous fluids as appropriate, if subject presents with severe dehydration administer octreotide
5. Perform stool work-up, CBC, electrolytes and other tests as appropriate
6. Administer antibiotics as needed (example fluoroquinolones), especially if diarrhea is persistent beyond 24 hours or there is fever or Grade 3-4 neutropenia

Hold lapatinib and chemotherapy (if applicable) until symptoms resolve to \leq Grade 1 (without complicating features) and reintroduce lapatinib at a reduced dose (unless dose had been reduced to 750mg, contact *medical monitor for further guidance*): **INFO:** FOR ISS: remove the italicized guidance

[figure not shown]
7. Supportive care and other interventions should be continued until diarrhea free (i.e., <Grade 1/bowel patterns returned to baseline) for 24 hours
8. Intervention may require hospitalization for subjects most at risk for life threatening complications

II.CTCAE Grade 4

1. Subject must call physician immediately for any Grade 4 diarrhea event
2. Hold treatment with lapatinib, hold chemotherapy or other concurrent anticancer therapy (if applicable)
 - Contact the Medical Monitor to discuss the patient case history and the possibility of re-initiation of study treatment, including dose modifications, following resolution of diarrhea (\leq Grade 1)

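### After grade 3–4 toxicity, section 5.2.3 restarts lapatinib at 1000 mg every 12 hours: 2000 mg a day, 1.6 times the starting dose and twice the dose in section 3.0

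*Combined protocol and SAP*

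**What the plan says.** Section 5.2.3 (Lapatinib Dosing) sets the starting dose at 1250 mg every 24 hours. It then has two rules for toxicity.

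- **Recurrent grade 1–2 toxicity:** two reductions are allowed, "Lapatinib 1000 mg PO every 24 hours continuously and Lapatinib 750 mg PO daily".
- **Grade 3–4 toxicity:** after a break of up to 14 days and resolution, "the study drugs may be resumed at a reduced dose (Lapatinib 1000 mg PO every 12 hours continuously".

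Section 3.0 (Study Design) covers the same grade 3–4 situation for both drugs: they may be "resumed at a reduced dose (Lapatinib 1000 mg PO daily continuously and Veliparib 150 mg PO every 12 hours continuously".

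Other lapatinib instructions for this trial:

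- Section 3.0 allows a "new 20 patient cohort using Lapatinib 1000 mg PO a day and Veliparib 150 mg PO twice a day" if the first cohort proves too toxic.
- Appendix I, on recurrent grade 2 diarrhea, says to "consider reducing the dose of lapatinib by 250mg or 1 tablet".
- Appendix I, on diarrhea of any grade, tells staff to "check they are taking lapatinib correctly, i.e. single daily dose, rather than splitting it through the day".

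The protocol does not say which section prevails when they differ.

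**The concern.** The step that 5.2.3 calls a reduction raises the daily dose, and it contradicts section 3.0. Staff who look up the restart dose in the section devoted to lapatinib, and follow it literally, would put a patient recovering from severe toxicity on more lapatinib than she was taking when the event occurred.

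The protocol's own background suggests that this could harm. Section 2.6 reports that diarrhea became more frequent as the dose rose, that "Doses of 500 and 750 BID were better tolerated than 900 mg BID", and that "Administration of the same daily dose in a BID schedule results in 2-fold greater systemic exposure than a QD schedule".

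There are also consequences for the trial, though smaller ones. Under both 3.0 and 5.2.3, a recurrence after restart takes the patient off study. A restart at too high a dose could therefore cause avoidable removals, and treatment tolerance is part of the primary objective. Section 5.3 measures compliance against the number of pills that were due, so the two sections also imply different denominators.

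**Working it through.** The plan states no daily total for this step, so there is no stated total to reproduce. The check converts each instruction to a daily dose and compares it with the start.

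**Inputs:** starting dose 1250 mg every 24 hours (3.0 and 5.2.3); restart dose 1000 mg every 12 hours (5.2.3) or 1000 mg daily (3.0); 250 mg tablets (5.2.1); highest phase I doses named, 1800 mg once daily and 900 mg twice daily (2.6).

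**Formula:** daily dose = dose × 24 / interval in hours; ratio = daily dose / 1250; tablets = daily dose / 250.

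| Instruction | Daily dose | Ratio to start | Tablets a day |
|---|---|---|---|
| Start (3.0, 5.2.3) | 1250 × 24/24 = 1250 mg | 1.0 | 5 |
| First reduction, recurrent grade 1–2 (5.2.3) | 1000 × 24/24 = 1000 mg | 0.8 | 4 |
| Second reduction (5.2.3) | 750 × 24/24 = 750 mg | 0.6 | 3 |
| Restart after grade 3–4 (3.0) | 1000 × 24/24 = 1000 mg | 0.8 | 4 |
| Restart after grade 3–4 (5.2.3) | 1000 × 24/12 = 2000 mg | 1.6 | 8 |

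**Against section 3.0:** 2000 / 1000 = 2.0.

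**Against the phase I doses:** 900 × 2 = 1800 mg a day, the same total as the top once-daily dose, and 2000 / 1800 = 1.11. The written restart dose is above both.

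**Exposure (illustrative only):** if exposure is proportional to dose and the schedule has no effect, it would be 1.6 times that at the start. If the 2-fold effect of twice-daily dosing in section 2.6 also applies, it would be 1.6 × 2 = 3.2 times. Section 2.6 says only that exposure generally rises with dose and that absorption is highly variable, so 3.2 is neither an estimate nor a ceiling.

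**Compliance:** if the 5.2.3 dose set the number of pills due, a patient correctly taking the section 3.0 dose would score 4 / 8 = 0.50, below the 0.75 threshold in section 5.3. Two such counts would mean removal.

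**Likely origin:** the matching veliparib sentence in 5.1.5 gives 150 mg every 12 hours, which is 300 mg against 400 mg a day at the start, a true reduction (300 / 400 = 0.75). The 12-hour interval was probably copied from there. That is inference; the contradiction does not depend on it.

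**The case against.** The strongest reply is that the error gives itself away. The sentence calls the dose reduced, the same paragraph has 1000 mg every 24 hours as its first reduction, and the next paragraph tells patients to take lapatinib once a day at about the same time. Sections 3.0 and Appendix I agree. This is a single site whose principal investigator holds the IND, and staff would have to hand out 8 tablets in place of 5 and call that a reduction. This stands as an argument that harm is unlikely. It does not make the instruction correct.

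Several limits on reach also stand:

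- **Cause.** The trigger is any grade 3–4 toxicity on two drugs, and veliparib may be responsible.
- **Restart barred.** The rule cannot apply after a grade 3–4 LVEF decrease or interstitial pneumonitis (6.2.3), or after severe liver changes (5.2.2).
- **Diarrhea.** Appendix I separately calls for a reduced dose after grade 3 diarrhea. Its text gives no figure for that restart, so staff may still turn to 5.2.3. Its 250 mg step belongs to recurrent grade 2 diarrhea and states no frequency; it supports the size of a reduction, not the interval.
- **Primary rate.** Most affected patients already count as a toxicity. The rate could change only where the first event falls outside the definition, such as uncomplicated grade 3 neutropenia, or grade 3–4 fatigue or anorexia as sections 3.0 and 7.6 define it.
- **Pharmacokinetics.** Section 6.3 places sampling on days 1–3 and 8–10 of cycle 1, which suggests a small effect. Section 7.5.3 also plans cycle 2 summaries and possible pre-dose plots to week 5, so a small effect is not assured.

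**Conclusion.** The concern holds: section 5.2.3 is wrong as written. The firm figures are dose ratios: 1.6 times the starting dose, 2.0 times the section 3.0 restart dose, and 1.11 times the highest phase I daily dose named. They need no assumption beyond reading the text literally. The exposure multiples do rest on assumptions, and the conclusion does not need them.

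The intended dose is clear from the rest of the protocol: 1000 mg once daily. How many patients would meet the rule is uncertain. As one illustration, Appendix I gives grade 3 diarrhea in 6% of patients on lapatinib alone; if that rate carried over to the combination, 20 × 0.06 = 1.2 patients would be expected from that cause alone.

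As a statistical matter the effect is minor. It must be fixed because it is a live dosing instruction that, taken literally, escalates the dose after severe toxicity.

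**What to change.** In section 5.2.3, change the lapatinib restart dose after grade 3–4 toxicity to 1000 mg every 24 hours. That is 4 tablets a day, 0.8 times the starting dose, and it matches section 3.0 and the first reduction already in 5.2.3.

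The cost is one corrected interval, issued as a protocol amendment or clarification letter to the single site. Sample size, endpoints and analysis do not change.

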5.1.5 Veliparib Dosing

The daily dose of Veliparib will be 200 mg PO every 12 hours continuously for 28 days (a cycle), starting on Day 2 Cycle 1. Patients developing grade 1 and 2 toxicities will be permitted to take a drug holiday of up to 14 days; after the drug holiday, if the adverse event has resolved to the satisfaction of the investigator, the study drug may be resumed at the same level. In the event of recurrent toxicity, there will be two dose reductions permitted (Veliparib 150 mg PO every 12 hours continuously and Veliparib 100 mg PO every 12 hours continuously). If the adverse event recurs, the patient will be taken off the study. Patients developing grade 3 and 4 toxicities will be interrupted for permitted for up to 14 days; after the drug holiday, if the adverse event has resolved to the satisfaction of the investigator, the study drugs may be resumed at a reduced dose (Veliparib 150 mg PO every 12 hours continuously). If the adverse event recurs, the patient will be taken off the study. **Veliparib will start on day 2.**

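### Section 5.2.3 prints the lapatinib dose after a grade 3–4 toxicity as 1000 mg every 12 hours, 60% above the starting dose; the fixed resumption dose elsewhere is ambiguous for patients already at that level

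*Combined protocol and SAP*

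**What the plan says.** Doses below are written as lapatinib mg daily / veliparib mg every 12 hours.

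- **Section 5.2.3** starts lapatinib at 1250 mg every 24 hours. For recurrent lower-grade toxicity, "there will be two dose reductions permitted (Lapatinib 1000 mg PO every 24 hours continuously and Lapatinib 750 mg PO daily". For grade 3–4 toxicity, after a break of up to 14 days, "the study drugs may be resumed at a reduced dose (Lapatinib 1000 mg PO every 12 hours continuously".
- **Section 3.0**, for the same grade 3–4 situation: "the study drugs may be resumed at a reduced dose (Lapatinib 1000 mg PO daily continuously and Veliparib 150 mg PO every 12 hours". For recurrent toxicity it also defines a lower level: "dose reduction minus two will be Lapatinib 750 mg PO daily and Veliparib 100 mg PO every 12 hours continuously".
- **Section 5.1.5** gives the veliparib half only: "the study drugs may be resumed at a reduced dose (Veliparib 150 mg PO every 12 hours continuously".
- **Section 3.0, lower-dose cohort paragraph.** If the toxicity boundary is met within the first 5 patients, the investigators may "open a new 20 patient cohort using Lapatinib 1000 mg PO a day and Veliparib 150 mg PO twice a day". On how those patients are then managed, the paragraph says: "The new cohort will follow the same rules used in the original cohort (Cohort -1". It restates the handling of grade 1–2 and recurrent toxicity, with one reduction: "dose reduction minus one will be Lapatinib 750 mg PO daily continuously and Veliparib 100 mg PO every 12 hours continuously". It gives no grade 3–4 resumption dose. Its off-study rule refers to recurrence after a second reduction, which this cohort does not have.

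In Sections 3.0, 5.1.5 and 5.2.3, recurrence of the adverse event after a grade 3–4 resumption takes the patient off study.

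**The concern.** The primary objective is safety and tolerance, and these sentences apply just after a severe toxicity. The lapatinib section calls a dose reduced when it is higher than any lapatinib dose level in the trial. It also disagrees with Section 3.0 and with the reduction a few lines above it. Section 8.4.3 asks for conduct exactly as the protocol describes, yet the protocol describes two different doses for one situation.

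The second issue is that the resumption dose is a fixed figure rather than a step down from the current dose. It works from the starting dose. For someone already at 1000/150, the literal text resumes the dose at which the event occurred. The lower-dose cohort starts at exactly that level, and it opens only if the higher doses have proved too toxic.

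**Working it through.** **Inputs.** Tablet strength 250 mg (5.2.1). Start 1250 mg, stated as 5 tablets a day (5.2.3). Dose levels 1250/200, 1000/150 and 750/100 (3.0). Lower-dose cohort start 1000/150 (3.0). Lapatinib background (2.6): twice-daily dosing doubles exposure at the same daily dose; 900 mg twice daily was less well tolerated than 500 or 750 mg twice daily; once-daily doses up to 1800 mg were generally well tolerated.

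**Plan's own figure.** 1250 / 250 = 5 tablets a day, as stated.

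**Printed lapatinib resumption dose.** Daily dose = single dose × 24 / interval.

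- As printed: 1000 × 24/12 = 2000 mg/day; 2000/250 = 8 tablets.
- Against the start: 2000/1250 = 1.60 (+60%).
- Against the dose in Section 3.0: 2000/1000 = 2.00.
- With a 24-hour interval: 1000 × 24/24 = 1000 mg/day; 1000/250 = 4 tablets; 1000/1250 = 0.80 (−20%). This agrees with Section 3.0.

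**Against the background data.** 2000/1800 = 1.11 and 1000/900 = 1.11, so the printed dose is 11% above the highest once-daily and the highest twice-daily dose described in Section 2.6. Exposure relative to 1250 mg once daily would be 2 × 1.0 = 2.0-fold if exposure did not rise with dose, and 2 × 1.60 = 3.2-fold if it were dose-proportional. Both are assumptions. Section 2.6 says that exposure generally rises with dose, so the lower end is cautious. The finding does not rest on this range.

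**Pill count.** Section 5.3 divides pills taken by pills due, with a threshold of 0.75. A patient correctly taking 4 tablets would score 4/8 = 0.50 if 5.2.3 as printed set the denominator.

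**Fixed 1000/150 against the current dose.**

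| Current level | Lapatinib | Veliparib |
|---|---|---|
| 1250/200 | 1000/1250 = 0.80 (−20%) | 150/200 = 0.75 (−25%) |
| 1000/150 | 1000/1000 = 1.00 (0%) | 150/150 = 1.00 (0%) |

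One level down from 1000/150 would be 750/1000 = 0.75 (−25%) and 100/150 = 0.67 (−33%).

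**Chance that the lower-dose cohort can open.** The boundary within 5 patients is 3 of 3, 4 of 4 or 4 of 5. A patient sequence that reaches 4 of 4 has already stopped at 3 of 3, so P = p³ + 3p⁴(1 − p).

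- At p = 0.30: 0.0270 + 0.0170 = 0.044.
- At p = 0.60: 0.2160 + 0.1555 = 0.37.

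**The case against.** **It is an obvious slip.** The sentence itself calls the dose reduced, the rest of 5.2.3 is once daily, Section 3.0 has the right figure, and Appendix I expects a single daily dose. This stands as an account of how the error arose. A reader might infer that the plan intends to escalate lapatinib after severe toxicity, and the documents do not support that. The printed number is still wrong at every dose level, in the section where a prescriber would look it up.

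**It does not reach every first grade 3–4 event.** This also stands. Severe liver changes (5.2.2) and grade 3–4 ejection-fraction decrease or pneumonitis (6.2.3) lead to stopping, and complicated diarrhea has its own rule in Appendix I. The printed dose matters for the remaining grade 3–4 events.

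**The lower-dose cohort has no printed rule that denies a reduction.** This stands too. In the main cohort the grade 3–4 resumption dose equals the first reduction level. The cohort paragraph redefines that level as 750/100, so carrying over the same rules could mean 750/100. But the text ties 750/100 to recurrent toxicity, and the only grade 3–4 figure available to carry over is 1000/150. Both readings are open. A reader might infer that the cohort is definitely denied a reduction; the documents do not settle that.

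**Few main-cohort patients are affected.** True: the same event recurring after a grade 3–4 resumption takes the patient off study. That leaves patients already reduced who then have a new or different grade 3–4 event. A reader might also infer that someone at 750/100 must go up to 1000/150 (1000/750 = 1.33, 150/100 = 1.50). The requirement that the dose be reduced contradicts that, so it is not an instruction to escalate.

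**Discretion protects patients.** Resumption is optional, and Sections 4.3 and 6.4 let the physician or principal investigator stop treatment. Neither supplies a correct resumption dose.

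**Conclusion.** The main point holds. The grade 3–4 lapatinib resumption dose in Section 5.2.3 is wrong as printed: 2000 mg/day, 60% above the start and twice the dose in Section 3.0. The cause is probably a slip, and the reach is limited to events outside the withdrawal rules and the diarrhea guideline. The arithmetic needs no assumption.

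The secondary point holds as an ambiguity. Read literally, the fixed 1000/150 in Section 3.0, with its veliparib half in 5.1.5, is a 0% reduction for the lower-dose cohort at its starting dose and for the few main-cohort patients already at that level. For the cohort, this depends on how the same-rules sentence is read. The cohort is unlikely to open if the regimen is tolerable (4.4% at a 30% toxicity rate). It can open with probability 37% at 60%, which is the situation it was written for. The number of already reduced main-cohort patients cannot be estimated from the documents and is likely to be small.

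**What to change.** 1. In Section 5.2.3, change the grade 3–4 lapatinib resumption dose to 1000 mg every 24 hours.
2. In Sections 3.0, 5.1.5 and 5.2.3, state that resumption after a grade 3–4 event is one level below the current level on the sequence 1250/200, 1000/150, 750/100. In the lower-dose cohort paragraph, state that this means 750/100.
3. In the same paragraph, make the off-study rule apply to recurrence after reduction to 750/100, in place of the reference to a second reduction.
4. Say that the existing withdrawal rules and the diarrhea guideline take precedence. Leave Appendix I unchanged.

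I would not add mandatory discontinuation at 750/100. Appendix I refers complicated diarrhea at lapatinib 750 mg for further guidance, and a blanket rule would conflict with it. A new veliparib step in Appendix I would be a separate design decision.

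The cost is one amendment with text changes in four places: the main text and the cohort paragraph of Section 3.0, and Sections 5.1.5 and 5.2.3. No patients, visits or procedures are added.
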